Study 1: Exploratory study - identifying the benefits of pMDI versus Diskus for delivering fluticasone/salmeterol combination therapy in patients with chronic obstructive pulmonary disease (COPD)

Version Date: 7 February 2014

Protocol

**Study 1: Exploratory study -
identifying the benefits of pMDI
versus Diskus for delivering
fluticasone/salmeterol combination
therapy in patients with chronic
obstructive pulmonary disease
(COPD)**

To characterise patients with COPD initiating with fluticasone/salmeterol combination therapy via pMDI and Diskus and to identify and compare the potential benefits of using either device in the delivery of fluticasone/salmeterol combination therapy

Contents

OBJECTIVES	3
BACKGROUND	3
DATASOURCE	4
STUDY DESIGN	4
STUDY OUTCOMES	7
STATISTICAL ANALYSIS.....	8
TIMELINE, DELIVERY AND COSTINGS	9
RESEARCH TEAM	9
REFERENCES.....	9

OBJECTIVES

The aims of this exploratory study are to characterise patients with chronic obstructive pulmonary diseaseⁱ (COPD) initiating with fluticasone/salmeterol combination therapy delivered via pressurised metered dose inhaler (pMDI; also known as Evohaler) or Diskus (also known as Accuhaler); and to identify and compare the potential benefits of using either device in the delivery of fluticasone/salmeterol combination therapy.

This will be carried out by:

- (1) Characterising patients with COPD on fluticasone/salmeterol combination therapy via pMDI and Diskus.
- (2) Identifying and comparing the potential benefits of using pMDI versus Diskus in the delivery of fluticasone/salmeterol combination therapy in terms of both efficacy and adverse events, in particular:
 - a. Number of COPD exacerbations
 - b. Development of pneumonia infections
 - c. Type II diabetes diagnosis
 - d. Therapeutic indexⁱⁱ
 - e. Number of severe COPD-related events, including:
 - i. Lower respiratory tract infections
 - ii. Oral thrush

These are more clearly defined under 'Dataset Variables' below.

BACKGROUND

Inhaled corticosteroid use by patients with obstructive lung disease is associated with increased risk of pneumonia [1], increased risk of developing type-II diabetes [2] and increased risk of oral thrush [3].

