- Development of pneumonia (recorded as absence/presence of, and confirmed via: chest X-ray within a month of a pneumonia diagnosis OR hospitalisation within a month of a pneumonia diagnosis). Note that baseline values will be zero due to study exclusion criteria.
- Development/progression of diabetes
 - Development of diabetes (recorded as absence or presence of) during outcome period for patients (for patients without diabetes at or prior to IPD)
 - Progression of ongoing type-II diabetes treatment to insulin (defined as no insulin prescription during 1 year baseline period AND any insulin prescriptions during 1 year outcome period)
 - Diabetic control (defined as change in HbA1c value prior to starting Seretide® and after IPD)
 - Diabetic medication (defined as change in anti-type-II diabetic medication dosage OR medication type)
- Number of potential severe COPD-related adverse events and date of event including
 - Oral thrush
 - Lower respiratory tract infections
 - Bronchitis
 - Dysphonia / hoarseness
 - Nasopharyngitis (common cold)
 - Sinusitis
 - Hypokalemia (low blood potassium)
 - Muscle or joint pain
- ICS dose (in outcome period only) and date of ICS prescription

Matching will be used if required.

STUDY OUTCOMES

The primary aim of the current study is to identify baseline and outcome characteristics of patients with COPD initiating with Seretide® combination therapy via pMDI and Diskus and to identify and compare the potential benefits of using each device in the delivery of Seretide®. Among other events, the effect of device on the following outcomes will be investigated:

(1) COPD related severe exacerbations

Where an exacerbation is defined as an occurrence^{vii} of:

- COPD-related: Unscheduled hospital admission / A&E attendance^{viii}; OR
- An acute course of oral steroids prescribed with evidence of a respiratory review^{ix};
OR

-
- b) Asthma/COPD review codes excl. any monitoring letter codes;
 - c) Lung function and/or asthma monitoring.

^{vii}Where ≥ 1 oral steroid course / hospitalisation / antibiotics prescription occur within 2 weeks of each other, these events will be considered to be the result of the same exacerbation (and will only be counted once).

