^{viii}**COPD-related Hospitalisations:** consist of either a definite COPD Emergency Attendance or a definite COPD Hospital Admission; OR a generic hospitalisation read code which has been recorded on the same day as a **Lower Respiratory Consultation*** (see below - excluding where the only lower respiratory code recorded on that day was for a lung function test).

^{ix}**Evidence of a Respiratory Review** - consists of the following:

- Antibiotics prescribed with evidence of a respiratory review^{ix}.

(2) COPD related adverse events

Where adverse events include the number of incidences of:

- Oral thrush
- Lower respiratory tract infections
- Bronchitis
- Dysphonia / hoarseness
- Nasopharyngitis (common cold)
- Sinusitis
- Hypokalemia (low blood potassium)
- Muscle or joint pain

(3) Therapeutic index

Therapeutic index = highest dose not causing harm (side effect) / lowest dose that causes benefit (reduced number of severe COPD-related events).

For the highest dose not causing harm: the median dose at which no (any) adverse events occur

For the lowest dose that causes benefit (reduced number of severe COPD-related events): median dose at which patients show no increase in number of exacerbations in outcome

STATISTICAL ANALYSIS

Statistically significant results will be defined as $p < 0.05$ and trends as $0.05 \leq p < 0.10$

Summary statistics will be produced for all baseline and outcome variables, as a complete dataset and by device. For variables measured on the interval or ratio scale, these will include:

Sample size (n) & percentage non-missing

Mean & Variance / Standard Deviation

Range (Minimum / Maximum)

Median & Inter-quartile Range (25th and 75th percentiles)

For categorical variables, the summary statistics will include:

Sample size (n)

Range (if applicable)

Count and Percentage by category (distribution)

Treatment arms will be compared using t-test / Mann Whitney U-test (depending on distribution) for variables measured on the interval/ratio scale and using a chi square test for categorical variables.

a) Any **Lower Respiratory Consultation*** (see below) and

b) Any additional respiratory examinations, referrals, chest x-rays, or events.

* **Lower Respiratory Consultations** - consist of the following:

a) Lower Respiratory read codes (including Asthma, COPD and LRTI read codes);

b) Asthma/COPD review codes excl. any monitoring letter codes;

c) Lung function and/or asthma monitoring.

TIMELINE, DELIVERY AND COSTINGS

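### The diabetic-medication variable is defined without direction, so it pools escalations with reductions, withdrawals and switches and does not isolate progression of diabetes

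*Protocol*

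**What the plan says.** In the Protocol, Study Design, Dataset Variables, the entry "Development/progression of diabetes" has four parts:

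- new diabetes in the outcome year, recorded as present or absent, in patients without it at or before the index date;
- "Progression of ongoing type-II diabetes treatment to insulin (defined as no insulin prescription during 1 year baseline period AND any insulin prescriptions" in the outcome year;
- glycaemic control, taken as the difference in HbA1c between before and after the index date;
- a treatment item, worded as "Diabetic medication (defined as change in anti-type-II diabetic medication dosage OR medication type".

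No other section restricts the last item to intensification, sets a minimum size of change or names categories of change. The Background explains why diabetes is measured: inhaled corticosteroid use is associated with "increased risk of developing type-II diabetes". The Objectives name only "Type II diabetes diagnosis". The Statistical Analysis section calls for counts and percentages by category and compares arms "using a chi square test for categorical variables".

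**The concern.** The parent entry is about diabetes appearing or getting worse, and the rationale in the Background is harm. The first two parts of the entry can go only one way. The HbA1c part is numeric, so its sign is kept. The medication part alone joins unlike changes, in dose or in drug, into one definition with no sign.

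A dose reduction is a change in dosage, and a swap between two comparable drugs is a change in medication type. Both satisfy the definition. So does stopping a drug, on the natural reading, although the Protocol does not spell that out. If the variable is coded as changed versus unchanged, the comparison between devices is of how often treatment was altered, not of how often diabetes progressed. At stake is how well this one variable can show a device difference in progression, and how its result would be read.

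**Working it through.** The Protocol gives no number of patients with diabetes, no rate of treatment change, no effect size and no power for this item, so there is no figure to reproduce. The check is on the definition, followed by arithmetic on assumed rates.

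**Set-up.** In each arm let E be the proportion escalating, R the proportion with a reduction or withdrawal and S the proportion with a substitution only. If each patient falls in one category, the proportion meeting the definition is A = E + R + S. The difference between arms is

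A1 − A2 = (E1 − E2) + (R1 − R2) + (S1 − S2).

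With R and S equal in the two arms, the last two terms are zero and the absolute difference is kept. The ratio A1/A2 moves towards 1 because the same amount is added above and below. The examples set S = 0; equal substitution would act exactly as equal reduction does.

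**Equal reductions (assumed).** E = 10% v 15%, R = 10% in each arm.
- Escalation only: 15/10 = 1.50, difference 5 points.
- Any change: 10 + 10 = 20% v 15 + 10 = 25%; ratio 25/20 = 1.25, difference still 5 points.

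**Opposite reductions (assumed).** E = 10% v 15%, R = 15% v 10%.
- Any change: 10 + 15 = 25% v 15 + 10 = 25%; ratio 1.00, difference 0.

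**Effect on power (assumed).** 500 patients with diabetes per arm, E = 20% v 12%, two-sided 5% test of two proportions without continuity correction. The Protocol gives the 0.05 level but not whether it is two-sided. With p1 and p2 the two arms' proportions, p̄ their mean, q = 1 − p and d = |p1 − p2|:

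power = Φ{[d√n − 1.96√(2p̄q̄)] / √(p1q1 + p2q2)}.

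For escalation only, p̄ = 0.16: [0.08 × 22.361 − 1.96 × √0.2688] / √0.2656 = (1.789 − 1.016) / 0.515 = 1.50, so power is 93.3%.

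| Reductions in the two arms | Any change | Difference | Risk ratio | Power | n per arm for 80% power |
|---|---|---|---|---|---|
| none (escalation only) | 20% v 12% | 8 points | 1.67 | 93.3% | 329 |
| 5% and 5% | 25% v 17% | 8 points | 1.47 | 87.5% | 406 |
| 10% and 10% | 30% v 22% | 8 points | 1.36 | 82.3% | 471 |
| 20% and 20% | 40% v 32% | 8 points | 1.25 | 75.1% | 564 |
| 5% and 9% | 25% v 21% | 4 points | 1.19 | 32.4% | 1737 |
| 5% and 13% | 25% v 25% | 0 | 1.00 | 5% (alpha) | none |

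Equal reductions cost some power. Only reductions that run opposite to escalations erode the difference itself, and it disappears only when the two gaps match (8 points each in the last row).

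**The case against.** A reader might infer that the Protocol scores reductions and withdrawals as worsening. It does not say so. Where this list wants a yes/no variable, as for pneumonia and new diabetes, it says presence or absence; the medication item has no such wording. The neighbouring HbA1c item is also worded simply as a change, and nobody would take a fall in HbA1c for a harm. A change in dose can likewise carry a sign, and a statistical analysis plan, which may exist but is not shown, could sort changes into increase, decrease and switch. This stands in part. The scoring as worsening is inferred from the parent entry. But dose and drug type are combined in one definition that the Protocol itself states, and that definition does not match the entry it sits under. A faithful analysis plan would inherit the mismatch.

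A reader might also infer that a real device difference would be cancelled or reversed. The documents give no rates that would support this. Cancellation needs reductions to differ between devices by as much as escalations, in the opposite direction, and reversal needs them to differ by more. A device that worsened glycaemic control could plausibly produce both more escalations and fewer reductions, so the pattern is possible, but nothing in the Protocol shows it.

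Finally, the item is peripheral. It is not in the numbered Study Outcomes, though that list is introduced as non-exhaustive. The Objectives mention only diagnosis, and the Background statement concerns developing diabetes rather than treatment changes in established disease. The insulin and HbA1c items already capture direction. All of this stands and limits the weight of the point.

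**Conclusion.** The definition is too broad for its purpose: as written it pools escalation with reduction, withdrawal and like-for-like switching and does not isolate progression. The expected consequence is dilution. With similar reduction rates in both arms the absolute difference is unchanged, while the risk ratio and power fall. The sizes shown rest wholly on assumed rates, an assumed number of patients with diabetes, one category per patient, and yes/no coding of the variable. Severity is low: the study is exploratory, this is one of four diabetes variables, and the other three are not affected in this way.

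**What to change.** Replace the definition with a classification of each patient with diabetes, comparing the outcome year with the baseline year:

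- escalation: dose increase of an anti-diabetic drug, or an added one;
- reduction or withdrawal;
- substitution;
- no change.

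Use escalation as the progression measure and report the other categories separately by device. Keeping substitution as its own category avoids having to rank drugs by intensity, at the price that a switch to a more intensive drug is not counted as escalation. State in advance how a patient with mixed changes, such as one drug increased and another stopped, is classified.

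The Protocol's data source already extracts prescribing information, so the cost is a revised definition and a little more coding. Fewer events will be counted, possibly many fewer if reductions and switches are common. In the equal-reductions example, events fall from 20% to 10% and from 25% to 15%, losses of 50% and 40%. In the opposite-reductions example they fall from 25% to 10% and from 25% to 15%, losses of 60% and 40%. The events removed are reductions, not progression. The change concerns only how recorded data are coded and touches no patient's treatment.

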STUDY DESIGN

The study will be a retrospective database analysis, consisting of a (one year) baseline period, a (one year) outcome period and an index date, defined as the date of the first prescription for Seretide[®] combination therapy at which patients with evidence of COPDⁱⁱⁱ will be split into the following groups:

- (1) Those using pMDI (also known as Evohaler)
- (2) Those using Diskus (also known as Accuhaler)

The baseline period will be one year prior to and including the index date^{iv} and it will be used for patient characterisation, such as demographics, baseline therapy, disease severity and number of COPD exacerbations. The outcome period will be one year following the index date, and the effect of device on COPD-related severe exacerbations, adverse events and therapeutic index will be investigated.

ⁱⁱⁱ COPD diagnostic code (at any time) and recorded spirometry data supporting COPD diagnosis within 5 years window of diagnosis code. Note that individuals with asthma and bronchiectasis will not be excluded.

^{iv} except for therapy prescribed at IPD (which is included in the outcome).

[figure not shown]

Figure 1: Study design

Inclusion Criteria

In order to be included in the study, patients must fit the following criteria:

- (1) COPD diagnosis (COPD diagnostic code (at any time) and COPD confirmed by FEV/FVC ratio <0.7 ever in medical history. Note that individuals with asthma and bronchiectasis will not be excluded)
- (2) Two years of continuous practice data comprising 1 year baseline data and 1 year outcome data
- (3) ≥2 prescriptions for Seretide® pMDI OR Seretide® Diskus during 1 year outcome period, inclusive of IPD (i.e. 1 Seretide® prescription at IPD plus ≥1 prescriptions for the same device during 1 year outcome period).
- (4) Age ≥35 at time of initiating with Seretide

Exclusion Criteria

- (1) Evidence of restrictive lung disease other than bronchiectasis (diagnostic code)
- (2) ≥1 prescription for inhaled corticosteroids (ICS), including as part of a fixed dose combination, during baseline period (excluding IPD)
- (3) Evidence of pneumonia during baseline period (diagnostic code)
- (4) No maintenance oral steroids in baseline

Dataset Variables

Demographics (gender, age, weight, height, BMI, smoking status, disease severity (FEV1 percent predicted, FEV1/FVC ratio, GOLD group, mMRC score)) will be calculated at (or closest to) the IPD. Disease severity will be regarded as missing if >5 years either side of IPD.

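### Starting fluticasone dose is captured, but no stated step conditions the device comparisons on it, so a dose imbalance between the arms could be read as a device effect

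*Protocol*

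**What the plan says.** **Eligibility and grouping (Protocol, Study Design).** Inclusion criterion 3 asks for at least two prescriptions of the same device, "i.e. 1 Seretide® prescription at IPD plus ≥1 prescriptions for the same device during 1 year outcome period". It names neither a strength nor a daily dose. At the index date patients are divided only by inhaler: "Those using pMDI (also known as Evohaler") on one side, Diskus on the other. Exclusion criterion 2 removes anyone with a "prescription for inhaled corticosteroids (ICS), including as part of a fixed dose combination, during baseline period (excluding IPD").

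**Where dose is recorded.** Under Dataset Variables, dose appears as "ICS dose (in outcome period only) and date of ICS prescription". Footnote iv defines the baseline year as including the index date, "except for therapy prescribed at IPD (which is included in the outcome"). Baseline treatment is taken from the year before the IPD.

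**Confounding control and tests.** Dataset Variables ends with one sentence: "Matching will be used if required". Statistical Analysis states: "Treatment arms will be compared using t-test / Mann Whitney U-test (depending on distribution"), with a chi square test for categorical variables. It also provides summaries of every baseline and outcome variable by device.

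**Role of dose.** The Background states: "Inhaled corticosteroid use by patients with obstructive lung disease is associated with increased risk of pneumonia". It says the same of type II diabetes and oral thrush. The therapeutic index under Study Outcomes is a ratio of two median doses, one tied to absence of harm and one to benefit.

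**The concern.** Because recent users of inhaled corticosteroid are excluded, a single prescription at the IPD sets both the device and the first fluticasone dose. If prescribers tend to start one device at a higher dose, device and dose are entangled from the first day. The protocol's own reasoning makes that matter: it links inhaled corticosteroid to the harms under study, and its therapeutic index is informative only if dose varies between patients and bears on harm and benefit.

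Run as written, the comparison of exacerbations, pneumonia, diabetes and adverse events is a crude contrast of two groups that may have started on different doses. Part or all of a difference could belong to dose and still be reported as the effect of device, which is the effect the study says it will investigate. An imbalance in the other direction could hide a real device difference.

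**Working it through.** **Step 1: what the text fixes.** The protocol states no sample size, event rate or dose distribution, so there is no figure to reproduce. Set side by side:

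- Strength at entry: unrestricted.
- Grouping: device only.
- Dose at the IPD: captured, since footnote iv counts that prescription in the outcome data and the dose line also records prescription dates.
- Between-arm tests: t-test, Mann-Whitney U or chi square, all unadjusted.
- Matching: optional, with no trigger, variables or method.
- Analyses that use dose: the therapeutic index only.

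So starting dose can be derived, but no stated step uses it when the other outcomes are compared.

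**Step 2: size of the distortion.** All inputs here are assumptions. There are two dose levels, no true device effect, and a high-versus-low dose risk ratio R of 1.3 to 1.7. The shares starting on the higher dose are s1 and s2 in the two arms. With risk p at the lower dose, an arm with share s has risk p × (1 + s(R − 1)). The risk p cancels:

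Apparent device RR = (1 + s2(R − 1)) / (1 + s1(R − 1))

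| Shares s1 vs s2 | R = 1.3 | R = 1.7 |
|---|---|---|
| equal | 1.00 | 1.00 |
| 50% vs 70% | 1.21 / 1.15 = 1.05 | 1.49 / 1.35 = 1.10 |
| 40% vs 80% | 1.24 / 1.12 = 1.11 | 1.56 / 1.28 = 1.22 |

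If the shares are swapped between devices, the ratios invert.

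**Step 3: effect on the p-value.** This takes a binary outcome, a two-sided 0.05 chi-square comparison and n patients per arm (all assumed). Let p1 and p2 be the arm risks, d = p2 − p1, and p̄ their mean. Then c = 1.96 × √(2p̄(1 − p̄)/n) and se = √((p1(1 − p1) + p2(1 − p2))/n). The probability of a significant result is 1 − Φ((c − d)/se) + Φ((−c − d)/se).

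Example: lower-dose risk 30%, R = 1.25, shares 40% vs 80%, n = 1000.
- p1 = 0.30 × 1.10 = 0.33 and p2 = 0.30 × 1.20 = 0.36, so d = 0.03.
- p̄ = 0.345, c = 0.0417 and se = 0.0212, so (c − d)/se = 0.549.
- The probability of a false device finding is 29.2%.

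| Lower-dose risk | R | Shares | n = 500 | n = 1000 | n = 2000 |
|---|---|---|---|---|---|
| 5% | 1.25 | 50% vs 70% | 5.3% | 5.7% | 6.3% |
| 5% | 1.5 | 40% vs 80% | 9.8% | 14.8% | 25.0% |
| 30% | 1.25 | 50% vs 70% | 7.9% | 10.9% | 17.0% |
| 30% | 1.25 | 40% vs 80% | 16.9% | 29.2% | 51.4% |
| 30% | 1.5 | 40% vs 80% | 49.4% | 78.6% | 97.3% |

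With equal shares, or with R = 1, every entry is 5.0%. The inflation runs from negligible (rarer outcome, modest imbalance) to severe (common outcome, large imbalance, large arms). The protocol does not say where in that range this study lies.

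**The case against.** The best defence is that the dose line is bookkeeping. With prior users of inhaled corticosteroid excluded, baseline dose is zero for everyone, so listing dose for the outcome year alone follows from eligibility. Pneumonia carries a similar note that its baseline values will be zero. This stands. A reader might infer from the line that starting dose is discarded or cannot be recovered; footnote iv and the dated prescriptions show otherwise.

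A reader might also infer that matching, even if done perfectly, could not align the arms on starting dose. The protocol does not support that either. It names no matching variables and does not rule out the IPD dose. Matching variables and covariates are commonly settled in a statistical analysis plan, which may exist and is not shown.

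Third, outcome-year dose will be summarised by device, so a large imbalance would probably be seen. This is true, but seeing an imbalance does not correct an unadjusted p-value.

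Fourth, the study is exploratory, and the protocol shows neither an imbalance nor its direction. This also stands, and it limits how strongly the point can be put.

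What survives is narrower. The protocol does fix unrestricted strength, grouping by device and unadjusted tests. Within what it states, nothing conditions the main comparisons on starting dose.

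**Conclusion.** The point holds as a low-cost improvement to the stated analysis; it does not demonstrate bias. The arms need not be aligned on starting fluticasone dose, and the tests as written could report a dose difference as a device difference in exacerbations, pneumonia, diabetes or adverse events. It applies less directly to the therapeutic index, which uses dose explicitly.

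Bias requires both a real imbalance in starting dose between devices and an effect of dose on the outcome. If both exist to the assumed degree, the apparent device risk ratio ranges from 1.05 (dose risk ratio 1.3, shares 50% vs 70%) to 1.22 (dose risk ratio 1.7, shares 40% vs 80%). If either is absent, it is 1.00. The wider split is one scenario and not an estimate for this population.

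**What to change.** Derive the prescribed daily fluticasone dose at the IPD and define it as an index (baseline) variable, separate from outcome-year dose. Tabulate it by device. Then match, stratify or adjust the device comparisons of exacerbations, pneumonia, diabetes and adverse events on it; any of the three would meet the point.

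Do not use post-index dose for this purpose. Dose changes during the outcome year may follow from exacerbations, side effects or the device itself, so conditioning on them could introduce a new bias.

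The cost is one derived variable from prescriptions already extracted, plus some loss of precision where a dose level is used with only one device and so offers no like-for-like comparison.

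### The exacerbation definition limits oral steroids to acute courses but not antibiotics, so maintenance antibiotic prescriptions that coincide with a respiratory review can be counted as exacerbations

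*Protocol*

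**What the plan says.** The definition has three branches and stands in two places with the same wording: Dataset Variables, footnote vi (used for both the baseline and the outcome year), and Study Outcomes, outcome (1).

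- Branch 1: a COPD-related unscheduled admission or emergency attendance.
- Branch 2: "An acute course of oral steroids prescribed with evidence of a respiratory review".
- Branch 3: "Antibiotics prescribed with evidence of a respiratory review".

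The de-duplication rule says that where steroid courses, hospitalisations or antibiotic prescriptions "occur within 2 weeks of each other, these events will be considered to be the result of the same exacerbation", they are counted once.

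Evidence of a respiratory review consists of (a) a lower respiratory consultation and (b) "Any additional respiratory examinations, referrals, chest x-rays, or events". Lower respiratory consultations include asthma or COPD review codes and "Lung function and/or asthma monitoring". No time window between prescription and review is given.

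On the population, inclusion criterion (1) says "Note that individuals with asthma and bronchiectasis will not be excluded", and exclusion criterion (1) carves bronchiectasis out of the restrictive-disease exclusion. Exclusion item (4), "No maintenance oral steroids in baseline", deals with maintenance treatment for steroids. Maintenance antibiotics have no counterpart anywhere in the protocol.

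**The concern.** For steroids the definition separates treatment of an acute event from background treatment. For antibiotics it does not. Patients with bronchiectasis, who are kept in on purpose, are a group in which long-term antibiotics are plausible, although the protocol gives no figure for how many receive them. A stable patient whose repeat prescriptions coincide with reviews could then appear as a frequent exacerbator.

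Two results depend on this count. Exacerbations are the first-listed outcome compared between devices. The denominator of the therapeutic index is the median dose among patients whose exacerbation count does not rise in the outcome year. A patient who starts long-term antibiotics in that year could be classed as worsening because of the prescriptions themselves.

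**Working it through.** The protocol states no event rate, sample size or antibiotic-use figure, so there is no figure to reproduce. The check is what the stated rules do to a regular series of prescriptions.

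**Inputs from the protocol:** a 1-year period (365 days), a 2-week (14-day) merging window, and the review condition on branch 3.

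**Assumed inputs, not in the protocol:** the interval between repeats; the share q of repeats with a qualifying review; the share p of an arm on such treatment.

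**Step 1: does the 2-week rule collapse repeats?** Place prescriptions on day 0 and at fixed intervals up to day 364, and merge neighbours no more than 14 days apart.

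| Interval (days) | Prescriptions | Episodes after merging |
|---|---|---|
| 7 | 53 | 1 |
| 14 | 27 | 1 |
| 28 | 14 | 14 |
| 56 | 7 | 7 |
| 84 | 5 | 5 |

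The single episode in the first two rows assumes that merging runs on from one prescription to the next. The last three rows do not depend on that reading, because each gap exceeds 14 days. For 28 days the count is 14 with day 0 included; 365/28 = 13.0, so the ceiling is 13 or 14.

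**Step 2: apply the review condition.** False events per patient-year on 28-day repeats = 14 × q.

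| q (assumed) | 0 | 0.1 | 0.25 | 0.5 | 1 |
|---|---|---|---|---|---|
| False events | 0 | 1.4 | 3.5 | 7 | 14 |

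**Step 3: effect on an arm's mean.** Rise = p × 14 × q. For p from 1% to 5%:

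- q = 0.1: 0.014 to 0.07 events per patient-year
- q = 0.25: 0.035 to 0.175
- q = 1: 0.14 to 0.70

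**Step 4: effect on the device difference.** With the same q in both arms, the spurious difference is (p1 − p2) × 14 × q. If p1 = p2 it is 0. If the shares were 3% and 1% (assumed), it is 0.02 × 14 × q = 0.28q: 0 at q = 0, 0.028 at q = 0.1, 0.07 at q = 0.25 and 0.28 at q = 1.

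**Step 5: effect on the therapeutic index.** A patient on the same repeats in both years, with a similar review pattern, has false events in both, and the change is about 0. A patient who starts 28-day repeats at the beginning of the outcome year gains 14q events; at q = 0.1 that is 1.4 on average. One net extra event is enough to remove a patient from the no-increase group.

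**The case against.** The strongest objection is that antibiotics alone are not enough. A prescription counts only with evidence of a respiratory review, which on a literal reading needs both a lower respiratory consultation and a further examination, referral, x-ray or event. A repeat issued without that evidence is not an exacerbation. This stands, and it rules out a stronger reading that a reader might infer: that every prophylactic prescription in a bronchiectasis patient is counted. The filter is nevertheless weak. Routine reviews and monitoring qualify as consultations, no time link is set, and the exclusion of days with only a lung function test applies to generic hospitalisation codes and not to antibiotics.

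A reader might also infer that the device comparison is biased. The protocol does not support that. It gives no figure for use of long-term antibiotics, for their linkage to reviews or for any imbalance between devices, and the artefact can be 0. The analysis would also blunt it. If counts are skewed, the Mann-Whitney test applies, and moving a net 2% of one arm from the middle to the top rank shifts the probability of superiority by only 0.02 × 0.5 = 0.01, however many false events each patient has. The therapeutic index uses a median, which a few reclassified patients would usually move little.

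There are partial safeguards. Each component is also analysed separately, so the hospital and steroid results are free of the problem. Bronchiectasis is recorded, baseline variables are summarised by device, and matching is available if required. These help to expose an imbalance, but none separates acute from maintenance antibiotics.

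Finally, code lists and repeat-prescription algorithms are often left to an SAP, which is not at hand. That covers the detail of an algorithm. It does not cover a definition that the protocol itself fixes, twice, with a limit on one drug class and none on the other.

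**Conclusion.** The point holds as a defect in a stated rule. As worded, maintenance or prophylactic antibiotic prescriptions that coincide with a respiratory review can be counted as exacerbations, and repeats more than 14 days apart are counted separately.

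The size cannot be fixed from the protocol. Per affected patient on 28-day repeats it runs from 0 to about 13 to 14 false events a year. Across an arm it depends on assumed prevalence and linkage, and it becomes a difference between devices only if affected patients are unevenly spread. If they are evenly spread, what remains is added noise, dilution of any real difference, and misclassification in the therapeutic index of patients who start such treatment in the outcome year. The change should be made because the inconsistency is plain and the correction is cheap; a demonstrated bias is not the reason.

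**What to change.** - In footnote vi and in outcome (1), put the words 'an acute course of' in front of antibiotics in the third branch, so that it matches the steroid branch, and keep the review condition.
- Prespecify a prescription-pattern rule that identifies long-term repeat antibiotics in the data. The study team should set its thresholds; the protocol gives no basis for particular values.
- Apply the rule identically in the baseline and outcome years, and record the prescriptions it identifies as background therapy, summarised by device.
- Report the exacerbation count under the definition as it now stands as a sensitivity analysis, so that the effect of the rule can be seen.

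The cost is a wording change in two places and one derivation on prescription data that the study already extracts. The downside is that a few genuine acute courses that resemble repeats, including some in frequent exacerbators, may be missed; the sensitivity analysis gives a bound on that loss.
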